#### 4.4.1 Training for assessor

The assessor will be trained to support reliable implementation of the conditioned pain modulation (CPM) test, short physical performance battery – balance subscale, and lower limb sensation test using a combination of webinars, pre-recorded videos, in person meetings, or written materials. Each coordinator will be required to perform each evaluation on a mock participant with the Study Chair or Study Chair's designee watching (in person or via video conferencing or via previously recorded videos submitted to the Research Base) in order to ensure correct implementation. The CPM test training may also involve evaluation of the consistency at which the coordinator increases the pressure using data from the device. These processes may be repeated at the Study Chair's request depending on performance. Once the Study Chair is satisfied with the coordinator's implementation, the coordinator will be certified to act as the blinded coordinator for the study. Ideally, the same assessor will perform the baseline and endpoint assessments for an individual participant.

### 4.4.2 Training for the unblinded coordinator

The unblinded coordinator will be trained using a combination of webinars, pre-recorded videos, in person meetings, or written materials to use a standardized script to support consistent introduction of the TENS device to the participant and to implement calibration of the TENS device. They will also be trained on how to create a Quell health App account using a de-identified Study Email for each participant. Each coordinator will be required to perform these processes on a mock participant with the Study Chair or Study Chair's designee watching (in person or via video conferencing or via previously recorded videos submitted to the Research Base) in order to ensure correct implementation. This process may be repeated at the Study Chair's request depending on performance. Once the Study Chair is satisfied with the coordinator's implementation, the coordinator will be certified to act as the unblinded coordinator for the study.

Participating coordinators/staff will be trained to screen, consent, and enroll patients prior to beginning the study. These activities can be performed by staff members other than the assessor and unblinded coordinator.

#### 4.5 Enrolling Participants

The Oncology Patient Enrollment Network (OPEN) is a web-based registration system available on a 24/7 basis. OPEN is integrated with CTSU regulatory and roster data and with the Lead Protocol Organization (LPOs) registration/randomization systems or Theradex Interactive Web Response System (IWRS) for retrieval of patient registration/randomization assignment. OPEN will populate the patient enrollment data in NCI's clinical data management system, Medidata Rave.

Requirements for OPEN access:

- A valid CTEP-IAM account;
- To perform enrollments or request slot reservations: Be on a LPO roster, ETCTN Corresponding roster, or PO roster with the role of Registrar. Registrars must hold a minimum of an AP registration type;
- If a Delegation of Tasks Log (DTL) is required for the study, the registrar(s) must hold the OPEN Registrar task on the DTL for the site; and
- Have an approved site registration for a protocol prior to patient enrollment.

To assign an Investigator (IVR) or Non-Physician Investigator (NPIVR) as the treating, crediting, consenting, drug shipment (IVR only), or receiving investigator for a patient transfer in OPEN, the IVR or NPIVR must list the IRB number used on the site's IRB approval on their Form FDA 1572 in RCR. If a

DTL is required for the study, the IVR or NPIVR must be assigned the appropriate OPEN-related tasks on the DTL.

Prior to accessing OPEN, site staff should verify the following:

- Patient has met all eligibility criteria within the protocol stated timeframes; and
- All patients have signed an appropriate consent form and HIPAA authorization form (if applicable).

Note: The OPEN system will provide the site with a printable confirmation of registration and treatment information. Please print this confirmation for your records.

Access OPEN at https://open.ctsu.org or from the OPEN link on the CTSU members' website. Further instructional information is in the OPEN section of the CTSU website at https://www.ctsu.org or https://open.ctsu.org. For any additional questions, contact the CTSU Help Desk at [name] or [contact].

The following additional information will be requested:

- a. Name of the unblinded coordinator
- b. Name of assessor

An email confirmation of registration will be forwarded.

## 5. RESEARCH PROTOCOL/STUDY PROCEDURES

### 5.1 Protocol Equipment Shipping Distribution

Upon receipt of the NCORP's IRB approval for this study, and upon request from the NCORP, the Research Base will ship a study start-up package. This request should be made through the study mailbox (i.e., *URCC\[contact]*). The start-up package will contain 1 conditioned pain modulation (CPM) test kit, 1 monofilament set, and 4 alternative size elastic bands for use with the TENS device. The CPM test kit will include a pressure algometer and test materials.

Each NCORP site will designate a research staff member to be responsible for receiving the study startup package. The staff member will verify that the shipment contains all supplies and that the supplies are in good condition. They will verify and record the identification numbers for accuracy. The Investigational Device Accountability Record (DARF) will be used to track supplies arriving from the URCC NCORP Research Base and CPM kits and monofilament sets shipped back to the URCC NCORP Research Base at the end of the study.

## 5.2 Study Device

TENS is listed as nonsignificant risk in the 2006 FDA's "Significant Risk and Nonsignificant Risk Medical Devices" Guidance. [51] The device that will be used in the study has been cleared by the FDA under K152954. It is currently legally marketed in the U.S. for the relief of chronic pain. Therefore, no IDE is necessary for this study. The device is a wireless transcutaneous electric nerve stimulation (TENS) device that emits a high frequency (i.e., 60–100 Hz) stimulation (waveform is biphasic with alternating leading phase). The device is controlled by an App that is available on Apple and Android devices. The device alternates between a 1 hour treatment period and 1 hour rest period on the continuous setting. Participants will be asked to wear the device for 5 hours per day on the continuous setting every day for 6 weeks. They will be asked to alternate the leg they wear it on each day in order to minimize potential skin reactions.

The active device emits electrical stimulation for the entire 1 hour treatment period, resulting in 3 hours of

total stimulation in 5 hours of wear. The dosing of the active arm was increased from the minimum dosage in our pilot study to maximize the amount of TENS stimulation since longer duration of stimulation has been linked to larger effect.[52] Additionally, the company that manufactures the device encourages individuals to use the device for at least 3 sessions per day based on the usage data and pain relief results that they have collected from their App data. This prescription is likely acceptable to participants based on participant feedback from our pilot (see **Feasibility section 1.4**). The unblinded research coordinator will walk the participants through the device's calibration process, which sets the intensity at 1.8 times the participant's sensation threshold. Participants in the active group will then be instructed to increase the intensity of the stimulation to the point that it is slightly below the intensity that is uncomfortable. The device will then remember the personalized intensity setting established at this initial visit for subsequent treatment sessions. However, participants will be allowed to control the intensity of the stimulation using the App throughout the study. The strategy of asking participants in the active group to increase the intensity until the stimulation is as strong as possible without being uncomfortable is based on previous research indicating that the strongest tolerable stimulation is the most effective.[28]

The identical looking placebo device emits 2 minutes of stimulation with a 30 second ramp down of intensity followed 57.5 minutes of no stimulation in the treatment session, which results in 7.5 minutes of stimulation in 5 hours. The placebo dose is designed to minimize TENS exposure but enhance blinding. We have shown that a brief stimulation provided by a placebo device blinds participants better than a device with no stimulation.[53] Participants in the placebo group will not be prompted to increase the stimulation until it is strong but comfortable because the stimulation will not continue sufficiently long after the calibration process to do so.

## 5.3 Schedule of study procedures

# 5.3.1 Screening / Consent Visit (Day -7; -2/+3 days) (approximately 1 hour)

Eligible participants who provide informed consent will be registered and given the daily diary of CIPN symptoms and rescue pain medication consumption, and trained on how to complete it at home during the Baseline Week (i.e., between the Screening and Baseline Visits). They will complete the CPM test and lower limb sensation test. Chemotherapy treatment notes will be collected for all consented participants.

## 5.3.2 Reminder phone call (Day -2: -1/+1 business day)

A research staff member will call the participant to remind them of the date of their Baseline Visit and to bring the completed forms with them.

## 5.3.3 Baseline Visit (Day 0) (approximately 1 hour)

All participants will be randomized according to procedures in **Section 5.3.4** after they arrive for the baseline visit. They will complete the PROs, balance tests, CPM test, and lower limb sensation test. At this time the participants will be given the TENS device (see **Section 5.2** for details of the device) and sufficient electrodes for 6 weeks of the study. They will be trained on how to use the TENS device. Using a standardized script to limit variation in expectations, the unblinded coordinator will lead all participants through the calibration process to identify their ideal intensity setting. The unblinded coordinator will train the participants on how to use the device at home. The unblinded coordinator will also download the Quell Health Account App to the participant's smartphone or other device (e.g., iPad) and create a Quell Health Account using a de-identified Study Email for the participant. The Study Email will be NCORP19085xxx[xxx=participant ID number]@mail.com.

The coordinator will then train the participant to use the App to start the TENS therapy and to open the App at least 1x per day when their mobile device or tablet is connected to the internet so that their deidentified usage data will be uploaded to the cloud. Participants will be asked not to modify settings in the App other than the intensity on the main screen for the 6 weeks of the study. The usage data (i.e., number of sessions per day, time the device is on the skin, and the intensity of the last session that occurred before connecting the device to the internet) will be downloaded from the Quell Health Account by the TENS device manufacturer and provided to the research team for use in promoting adherence (see **Section 5.3.7 Phone calls**). The participants will be given a daily diary to complete during Weeks 4 (i.e., day 21 - 28) and 6 (i.e., day 35 - 42) in which they will record their daily symptoms and rescue pain medication consumption.

### 5.3.4 Randomization/Stratification

A computer-generated randomization schedule will be used to randomize participants 1:1 to the two intervention conditions stratified by study site in random block sizes of 2 and 4. The schedule will be prepared by a URCC NCORP Research Base biostatistician. The coordinator will use the Randomization form in REDCap to obtain the randomization assignment at the Baseline Visit.

The two study arms are as follows:

- a. Active TENS Device
- b. Placebo TENS Device

A total enrollment of 150 participants is planned, with up to 75 participants randomized to each intervention group. Note, that participants who discontinue prior to randomization (i.e., between the screening and baseline visits) will not be replaced. It should take approximately 12 months to accrue all participants.

Week	Screening And Registration	Randomization	Distribution of Study Device	Self- Report Measures	Functional Exam Measures	Coordinator open participant Quell App	Adverse Event Monitoring
Screening (Visit 1)	х						
Baseline (Visit 2)		х	х	Х	Х		
1							Х
2							
3							Х
4							
5							Х
6 (Visit 3)				Х	Х	Х	Х

Table 5. Schedule of Events\*

\*Daily diary completed between screening and baseline visit and during Weeks 4 (i.e., day 21 - 28) and 6 (i.e., day 35 - 42). Participants will be called 4 weeks after the end of the study (i.e., Week 10) and asked if they are using the commercial device).

## 5.3.5 Blinding

The active and placebo devices will look identical, light up in the same manner, and have identical packaging. We have shown that a brief stimulation provided by a placebo device blinds participants better than a device with no stimulation.[53] Participants and the research coordinators who implement the assessments (i.e., the blinded coordinator or assessor) will be blinded to the treatment assignment. An unblinded coordinator will teach the participants to use the device, following an almost identical script for both treatment groups. The script will convey that some people feel the TENS sensation more than others and sometimes the sensations fade over the duration of a treatment session. There will be 2 additions to the script for the active group. First, a section asking the participants to increase the stimulation after the initial device calibration until it first feels uncomfortable and then turn the intensity down one click (i.e., 5%

of the stimulation strength) in order to obtain the optimal "strong but comfortable" stimulation intensity. Note, that this will not be done in the placebo group because the stimulation will not continue sufficiently long after the calibration process for this to happen. Second, a sentence suggesting that the active group may increase the intensity manually during the treatment sessions if desired. The unblinded coordinator will be available to troubleshoot difficulties with the device throughout the study. This modified double-blind design will maintain a blinded outcomes assessor by having an unblinded coordinator who can respond to participants' questions that could reveal the participants' group assignments. The participants will be instructed not to discuss any aspect of the TENS device with the blinded coordinator or other participants in the study. The coordinators will be instructed not to discuss the details of the placebo device with the participants. The unblinded coordinator and the assessor will be instructed not to discuss details of study participants with each other. Blinding success will be assessed (see measures).

# 5.3.6 At home procedures (Days 21-28; 35-42)

Participants will complete a daily diary including the CIPN Symptom Inventory and consumed rescue analgesic medication (i.e., acetaminophen (Tylenol) or NSAIDs). They will be asked to complete it before bedtime when they are not wearing the device during weeks 4 and 6.

# 5.3.8 End of Study Visit (Day 42; +/- 5 days) (approximately 1 hour and 15 minutes)

All participants will complete the patient-reported outcome measures, balance tests, conditioned pain modulation test, and lower limb sensation test. The coordinator will also review the list of medications that the participant reported using for CIPN at the beginning of the study and ask the participant if they changed dosages of any of the medications. Any changes will be recorded in the Changes in concomitant analgesic medications form. The coordinator will ask the participant for their device and open the Quell App to ensure final data transfer to the cloud. The data will then be downloaded by the device manufacturer and sent to the Research Base. If the participant does not come to the Week 6 visit, the coordinator will call them up to 3 times to try to reschedule the visit. The rescheduled visit can occur up to 1 month after the date of the 6-week visit. If the participant agrees to come back in, they will be encouraged to keep using the device until the rescheduled visit date.

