## 1.2 Literature Review

**TENS is a promising therapy for CIPN.** TENS is the application of electrical stimulation through the skin. It is a safe, non-pharmacologic, non-addictive, and inexpensive therapy used clinically for pain control. The waveform, frequency, and maximum current of the electrical stimulation vary among devices, but the proposed mechanisms of action are similar.[28] Evidence suggests that TENS reduces central excitability and activates descending inhibition, both of which have been implicated in CIPN in animal studies and one small human study. In animal models, TENS reduces the enhanced central excitability of nociceptive neurons induced by inflammation and nerve injury[33] and decreases the release of the excitatory neurotransmitter glutamate in the dorsal horn of the spinal cord.[32] TENS also produces analgesia in animal models by activating descending inhibition in the brainstem and spinal cord through activation of

endogenous opioid receptors.[30, 31, 34] Consistently, human studies show opioid receptor activation by TENS during pain inhibition[35] and show that TENS restores descending inhibition in individuals with fibromyalgia during a single TENS session.[29]

**TENS** is efficacious for chronic pain and promising for non-painful neuropathy symptoms in other conditions. The efficacy of TENS for pain is supported by its widespread clinical use as well as positive results from RCTs in various chronic pain conditions, including peripheral neuropathic pain.[29, 36-46] However, these RCTs are generally small and not blinded. RCTs including patients with diabetic peripheral neuropathy showed improvements in discomfort and in a composite neuropathy score that includes ratings of pain, numbness, and prickling sensations,[36, 37] suggesting that TENS could also reduce non-painful neuropathy symptoms. Furthermore, dysmenorrhea and writer's cramp, for which RCT data supports the efficacy of TENS [41, 43, 45] involve cramping pain, and our preliminary results suggest that CIPN-related cramping may be particularly responsive to TENS (Table 1).

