## 10.6 Exploratory Analyses.

(1) ANCOVA analysis as in the primary will be used to investigate the effects of TENS on exploratory outcomes (i.e., balance (SPPB balance subscale), descending inhibition (CPM test), physical function (PROMIS short form), CIPN-interference in daily life, CIPN measured by TNAS and CIPN symptom inventory composite measure, depression and anxiety (PROMIS short forms)) at baseline and at Week 6 visits.

(2) Analysis of variance (ANOVA) or an appropriate non-parametric method (e.g., Wilcoxon test) if the normality assumption is not satisfied will be used to evaluate the between arm differences in participant-perceived changes in CIPN symptoms and participant-perceived change in ability to be active.

(3) Descriptive statistics will be used to characterize the distribution of descending inhibition as measured by CPM at baseline. Additionally, the correlation of descending inhibition with CIPN severity (via CIPN20, TNAS, and symptom NRS scores) will be evaluated using a Spearman's correlations.

(4) To explore the predictive effects of baseline descending inhibition on response to TENS, ANCOVA analysis will be used to investigate whether baseline descending inhibition predicts the effect of TENS on CIPN. The model will include CIPN20 at Week 6 as the outcome, baseline CPM test result, treatment group, and baseline CPM test result x treatment group interaction as factors, and study site and the baseline CIPN20 score as covariates.

(5) To explore mechanistic associations between changes in descending inhibition and CIPN symptoms, we will use mediation analysis technique (the method initially formalized by Baron and Kenny, extended to clinical trial settings by Kraemer, and methodologically updated by MacKinnon et al.). Specifically, we will use path modeling to estimate indirect (mediation) effects of changes in the CPM test on CIPN symptoms, and bootstrapping to estimate the 95% confidence intervals. The MPlus software will be utilized.

(6) The proportion of participants who decreased "as-needed" usage of acetaminophen and NSAIDs (defined as taking acetaminophen or NSAIDs, on average, at least 30% fewer days per week in the last week of the trial compared to the baseline week) will be compared by groups using a Chi-Square test.

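### The Week 6 CPM test has no stated device-use condition and no record of time since the last session, so acute and sustained effects of TENS on descending inhibition cannot be told apart

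*Combined protocol and SAP*

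**What the plan says.** Section 5.3.8 lists the Week 6 assessments: "All participants will complete the patient-reported outcome measures, balance tests, conditioned pain modulation test, and lower limb sensation test". It adds no condition on device use beforehand. Section 5.4 fixes the water temperature, the immersion time and the number of pressure readings for CPM, but not whether the device is on or when it was last used.

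Participants are still on treatment at this visit. Section 5.2 states: "Participants will be asked to wear the device for 5 hours per day on the continuous setting every day for 6 weeks". No clock time is set. If the visit is rescheduled, 5.3.8 says that "they will be encouraged to keep using the device until the rescheduled visit date".

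In the background, section 1.2 cites human evidence that "TENS restores descending inhibition in individuals with fibromyalgia during a single TENS session". For the symptom diary, section 5.3.6 does separate rating from wear: "They will be asked to complete it before bedtime when they are not wearing the device during weeks 4 and 6".

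CPM enters the exploratory ANCOVA in 10.6(1) and the mediation analysis in 10.6(5), where "we will use path modeling to estimate indirect (mediation) effects of changes in the CPM test on CIPN symptoms". Neither has a term for time since the last session.

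**The concern.** CPM is the protocol's measure of descending inhibition, and the protocol itself cites a within-session effect of TENS on that pathway. If such an effect also occurs in CIPN, a Week 6 CPM result may depend on how close the test falls to a session. The plan neither controls that interval nor plans to record it.

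At stake is the meaning of the exploratory CPM results. A difference between arms could reflect a lasting change after six weeks, a transient response to that day's session, or both. These call for different decisions on how to test the mechanism in a phase III trial. Exploratory Aim 1 (section 2.4) does not say which effect is sought.

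**Working it through.** The plan states no figure on this point, so the check is mainly a comparison of sections.

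1. **Is there a condition elsewhere?** Sections 5.3.8 and 5.4 give none for CPM. Section 5.9 bars use while driving and limits continuous wear, which bears on visit-day use only incidentally. Section 5.3.6 covers the diary only.

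2. **Does exposure differ by arm?** Five hours on the alternating setting (5.2) contains three one-hour treatment periods.
   - Active: 3 × 60 = 180 minutes of stimulation.
   - Placebo: 3 × 2.5 = 7.5 minutes, which matches the figure in 5.2.
   - Ratio: 180 / 7.5 = 24.

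   Any acute effect would fall almost wholly on the active arm, so it enters the arm contrast and randomization does not cancel it.

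3. **Do pre and post conditions match?** CPM is measured at Screening (5.3.1), before any device is issued, and at Baseline (5.3.3), where the tests are described ahead of the device hand-over. Week 6 is measured under ongoing daily use, at an unspecified interval from it.

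4. **What does the CPM contrast estimate?** Let S be the sustained effect, A the acute effect, and p the share of active participants tested while the acute effect is present. With effects additive and no acute effect under placebo, the contrast is S + p × A. The trial observes only the sum.
   - Illustration, with values assumed and not taken from the documents: S = 0, A = 0.5 SD, p from 0.2 to 0.6. The contrast runs from 0.2 × 0.5 = 0.10 SD to 0.6 × 0.5 = 0.30 SD. A contrast of 0.30 SD would look the same if S were 0.30 and p × A were 0.
   - Added variance in the active arm is p(1 − p)A²: 0.2 × 0.8 × 0.25 = 0.040 and 0.6 × 0.4 × 0.25 = 0.060, with a maximum of 0.0625 at p = 0.5. Under these assumptions that is about 4% to 6% of the CPM variance, so the noise is modest.

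5. **Could tests fall near a session?** Assume visits uniform from 08:00 to 17:00 and one unbroken five-hour wear block placed uniformly within waking hours (07:00–22:00 or 06:00–23:00), and ignore the driving restriction. Then about 41% or 38% of visits fall inside the wear block, and about 50% or 47% fall inside it or within two hours after. These are assumptions about behaviour. They show only that overlap is possible under the text.

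6. **Can it be separated afterwards?** The usage data listed in 5.3.3 are "number of sessions per day, time the device is on the skin, and the intensity of the last session" before the upload. Sections 5.4 and 5.11 list sessions per day and skin-contact time. Neither clock time nor leg is listed. Section 5.3.8 does secure a last upload: "The coordinator will ask the participant for their device and open the Quell App to ensure final data transfer to the cloud". Whether any session took place on the visit day may therefore be identifiable; the interval to the test is not among the planned items.

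7. **What happens to mediation?** An indirect effect is the product of the arm-to-CPM path and the CPM-to-symptom path given arm. Timing can shift the first. Timing variation unrelated to symptoms would tend to weaken the second.

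**The case against.** The strongest reply is that an effect measured under ordinary daily use is a legitimate target. Exploratory Aim 1 does not promise a sustained effect, treatment is daily, and the proposed mechanism includes activation within a session. On that view the Week 6 contrast is a valid randomized on-treatment comparison. This stands: mixed does not mean biased. But the plan does not say that this is the target, and without a common test condition the mixture depends on visit scheduling.

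Other replies also hold in part:
- The cited evidence concerns fibromyalgia and the session itself. It says nothing about how long the effect lasts, so dependence on time since the last session is an inference.
- The diary rule sets no interval. It is a precedent for having the device off, not for a washout.
- Assessor training materials (4.4.1) are not in the documents and might contain a test-day condition. The protocol does not require one.

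A reader might infer more than the documents support:
- **Acute effects on balance or monofilament threshold.** None is cited. CPM is measured at the trapezius and hand, so which leg was stimulated is not an issue for that test site.
- **A distorted arm difference in sensation.** Section 10.6(8) tests the proportion improved against no improvement and states no arm contrast. Sensation is not in the 10.6(1) list.
- **A false mediation finding.** This needs a further link between timing-driven CPM change and symptoms, which the documents do not describe.
- **Total loss of the information.** A coarse check by visit-day use may be possible from the usage data.

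**Conclusion.** The point holds for CPM. Followed as written, the plan takes Week 6 CPM in the active arm at uncontrolled intervals from stimulation and does not plan to record them, while the placebo arm receives almost none. The contrast in 10.6(1) and the mediator in 10.6(5) cannot be read as acute or as sustained, and they carry some added noise.

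The size and frequency are unknown. The figures in the illustrations are assumptions, and the 0.4 effect size in section 10.3 is no yardstick for them because it sizes the CIPN20 analysis. The point rests on the cited single-session effect carrying over to CIPN to some degree. It does not show that the CPM contrast is biased as an on-treatment effect, and it does not touch the primary CIPN20 analysis.

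Severity is minor because the affected outcomes are exploratory. It is worth acting on as a cheap improvement, since the missing information has to be collected at the visit.

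**What to change.** - In 5.3.8, state whether Week 6 CPM is meant to reflect an acute or a sustained effect.
- Set one common device-use condition for the Week 6 examiner-run tests: at least the device off the leg, as for the diary. Whether to add an interval, and how long, is for the investigators. Give the condition in the reminder already made at the Day 35 call (5.3.7).
- Have the unblinded coordinator record the time and leg of the last session on an existing Week 6 form, so that the assessor need not ask about the device.
- Add to 10.6 a sensitivity analysis of CPM by time since last session.
- For sensation, record the tested foot and the last-treated leg, as a precaution only. Section 5.4 names the big toe but not the side, and 5.2 has participants alternate legs daily.

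The cost is one instruction in an existing call, a few fields on existing forms, and one added exploratory analysis. The downside is that some visits will need timing around the day's sessions.
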